7.7.2 DINAMO Mono

Data from the empagliflozin Phase III study 1245.20 in adult patients with Type 2 Diabetes were analysed to derive estimates for the treatment failure rate based on the definition in DINAMO™ Mono. Restricted to a study population with a baseline HbA1c from 6.5% to 9.0% the treatment failure rates as in Table 7.7.2:1 were determined.

Table 7.7.2: 1 Treatment failure rate in 1245.20 based on endpoint definition for DINAMO Mono

	Frequency of treatment failure			
	Placebo N (%)	Empagliflozin 10 mg N (%)	Empagliflozin 25 mg N (%)	Sitagliptin N (%)
Analysed patients	207 (100)	195 (100)	201 (100)	203 (100)
Treatment failure	138 (67)	56 (29)	43 (21)	40 (20)

A treatment failure rate between 65% and 85% is expected in the placebo group in DINAMO™ Mono. The initial minimum sample size of 12 patients per group was chosen so that the upper limit of the 90% confidence interval for the risk difference would not include 0 for an approximate risk difference of 40% (see Table 7.7.2: 2).

Table 7.7.2: 2 Exact 90% confidence interval for risk difference scenarios in DINAMO Mono

N per group	Frequency of treatment failure			Exact 90% CI
	Placebo N (%)	Active treatment N (%)	Risk difference %	
6	5 (83.3)	1 (16.7)	-66.7	(-93.9, -12.4)
	5 (83.3)	2 (33.3)	-50.0	(-85.6, 5.5)
8	6 (75.0)	2 (25.0)	-50.0	(-82.0, -3.1)
	6 (75.0)	3 (37.5)	-37.5	(-73.6, 9.7)
10	8 (80.0)	3 (30.0)	-50.0	(-79.2, -8.7)
	8 (80.0)	4 (40.0)	-40.0	(-70.8, -0.5)
	7 (70.0)	3 (30.0)	-40.0	(-72.1, 1.6)
12	10 (83.3)	5 (41.7)	-41.7	(-69.4, -6.9)
	9 (75.0)	4 (33.3)	-41.7	(-70.9, -4.2)
	9 (75.0)	5 (41.7)	-33.3	(-63.2, 2.3)
	8 (66.7)	3 (25.0)	-41.7	(-70.9, -4.2)

New patient recruitment for DINAMO™ Mono was prematurely discontinued due only to patient recruitment difficulties. The initially planned recruitment period up to April 2022 was preserved, resulting in a sample size of approximately 20 patients in DINAMO™ Mono.

8. INFORMED CONSENT, TRIAL RECORDS, DATA PROTECTION, PUBLICATION POLICY

The trial will be carried out in compliance with the protocol, the ethical principles laid down in the Declaration of Helsinki, in accordance with the ICH Harmonized Tripartite Guideline for Good Clinical Practice (GCP), relevant BI Standard Operating Procedures (SOPs), the EU regulation 536/2014 and other relevant regulations.

Standard medical care (prophylactic, diagnostic and therapeutic procedures) remains in the responsibility of the treating physician of the patient.

The Investigator will inform the sponsor immediately of any urgent safety measures taken to protect the trial subjects against any immediate hazard, and also of any serious breaches of the protocol or of ICH GCP*.

The Boehringer Ingelheim transparency and publication policy can be found on the following web page: trials.boehringer-ingelheim.com. The rights of the Investigator and of the sponsor with regard to publication of the results of this trial are described in the Investigator contract. *As a rule, no trial results should be published prior to finalization of the Clinical Trial Report.*

The certificate of insurance cover is made available to the Investigator and the patients, and is stored in the ISF (Investigator Site File).

8.1 TRIAL APPROVAL, PATIENT INFORMATION, INFORMED CONSENT

This trial will be initiated only after all required legal documentation has been reviewed and approved by the respective Institutional Review Board (IRB) / Independent Ethics Committee (IEC) and competent authority (CA) according to national and international regulations. The same applies for the implementation of changes introduced by amendments.

Prior to patient participation in the trial, written informed consent must be obtained from one or both parents of the patient (or the patient's legally accepted representative) according to ICH GCP and to the local regulatory and legal requirements of the participating country. Each signature must be personally dated by each signatory and the informed consent and any additional patient/parent(s)-information form retained by the investigator as part of the trial records. A signed copy of the informed consent and any additional parent(s) information must be given to each parent or the patient's legally accepted representative.

In addition to this document, the patient will be provided with an information sheet adapted to his/her age group (two groups: from 10 to 14 years; from 15 to 17 years included). The version prepared for the younger patient should be used for the older patient if judged more appropriate by the investigator) where his/her assent will be collected according to the regulatory and legal requirements of the participating country. Except if the patient is unable to do it, he/she will have to sign or write his/her name on this document and to date it in the day she/he assents to participate.

It is important that the investigator ensure at each visit that the patient still assents to participate in the study. In addition, the refusal of the patient to participate must be accepted independently of the consent of his/her parent(s)/legal guardian.

The patient and his/her parent(s)/legal guardian must be informed that his/her personal trial-related data will be used by Boehringer Ingelheim in accordance with the local data protection law. The level of disclosure must also be explained to the patient and his/her parent(s)/legal guardian.

The patient and his/her parent(s)/legal guardian must be informed that the patient's medical records may be examined by authorized monitors (CTM/CRA) or Clinical Quality Assurance auditors appointed by Boehringer Ingelheim, by appropriate IRB / IEC members, and by inspectors from regulatory authorities.

Re-consenting may become necessary when new relevant information becomes available and should be conducted according to the sponsor's instructions. Re-consent can be done remotely/by telephone/telemedicine/in-home visit under exceptional circumstances due to the COVID-19 pandemic. The initial informed consent and assent at Visit 1A must be done in the clinic.

The consent and re-consenting process should be properly documented in the source documentation.

8.2 DATA QUALITY ASSURANCE

A quality assurance audit/inspection of this trial may be conducted by the sponsor, sponsor's designees, or by IRB / IEC or by regulatory authorities. The quality assurance auditor will have access to all medical records, the investigator's trial-related files and correspondence, and the informed consent documentation of this clinical trial.

8.3 RECORDS

Case Report Forms (CRF) for individual patients will be provided by the sponsor. See [Section 4.1.5.2](#) for rules about emergency code breaks. For drug accountability, refer to [Section 4.1.8](#).

8.3.1 Source documents

In accordance with regulatory requirements the investigator should prepare and maintain adequate and accurate source documents and trial records that include all observations and other data pertinent to the investigation on each trial patient. Source data as well as reported data should follow good documentation practices and be attributable, legible, contemporaneous, original and accurate. Changes to the data should be traceable (audit trail). Data reported on the eCRF must be consistent with the source data or the discrepancies must be explained. The current medical history of the patient may not be sufficient to confirm eligibility for the trial and the investigator may need to request previous medical histories and evidence of any diagnostic tests. In this case the investigator must make three documented attempts to retrieve previous medical records. If this fails a verbal history from the patient, documented in their medical records, would be acceptable.

Before providing any copy of patients' source documents to the sponsor the investigator must ensure that all patient identifiers (e.g. patient's name, initials, address, phone number, social security number) have properly been removed or redacted to ensure patient confidentiality.

If the patient is not compliant with the protocol, any corrective action e.g. re-training must be documented in the patient file. For the eCRF, data must be derived from source documents, for example:

- Patient identification: gender, date or year of birth (in accordance with local laws and regulations)
- Patient participation in the trial (substance, trial number, patient number, date patient and parent(s)/legal guardian was informed)
- Dates of patient's visits, including dispensing of trial medication
- Medical history (including trial indication and concomitant diseases, if applicable)
- Medication history
- Adverse events and outcome events (onset date (mandatory), and end date (if available))
- Serious adverse events (onset date (mandatory), and end date (if available))
- Concomitant therapy (start date, changes)
- Originals or copies of laboratory results and other imaging or testing results, with proper documented medical evaluation (in validated electronic format, if available)
- Completion of "Patient's Participation in the trial" (end date; in case of premature discontinuation document the reason for it).
- Prior to allocation of a patient to a treatment into a clinical trial, there must be documented evidence in the source data (e.g. medical records) that the trial participant meets all inclusion criteria and does not meet any exclusion criteria. The absence of records (either medical records, verbal documented feedback of the patient or testing conducted specific for a protocol) to support inclusion/exclusion criteria does not make the patient eligible for the clinical trial.

8.3.2 Direct access to source data and documents

The sponsor will monitor the conduct of the trial by regular on-site monitoring visits and in-house data quality review. The frequency of on-site monitoring will be determined by assessing all characteristics of the trial, including its nature, objective, methodology and the degree of any deviations of the intervention from normal clinical practice.

The investigator /institution will allow on-site trial-related monitoring, audits, IRB / IEC review and regulatory inspections. Direct access must be provided to the eCRF and all source documents/data, including progress notes, copies of laboratory and medical test results, which must be available at all times for review by the CRA, auditor and regulatory inspector (e.g. FDA). The CRA and auditor may review all eCRFs and informed consents. The accuracy of the data will be verified by direct comparison with the source documents described in [section 8.3.1](#). The sponsor will also monitor compliance with the protocol and ICH GCP.

Remote source data verification in exceptional cases at the time of restricted on-site monitoring visits due to a COVID-19 pandemic, when such decision has been taken centrally

for a trial, must first be discussed with the sponsor before implementation to ensure alignment with local regulations.

8.3.3 Storage period of records

Trial site(s):

The trial site(s) must retain the source and essential documents (including ISF) according to the national or local requirements (whatever is longer) valid at the time of the end of the trial.

Sponsor:

The sponsor must retain the essential documents according to the sponsor's SOPs.

8.4 EXPEDITED REPORTING OF ADVERSE EVENTS

BI is responsible to fulfil their legal regulatory reporting obligation and in accordance to the requirements defined in this CTP.

8.5 STATEMENT OF CONFIDENTIALITY AND PATIENT PRIVACY

Individual patient data obtained as a result of this trial is considered confidential and disclosure to third parties is prohibited with the exceptions noted below. Patient privacy will be ensured by using patient identification code numbers.

Data protection and data security measures are implemented for the collection, storage and processing of patient data in accordance with the principles 6 and 12 of the WHO GCP handbook. Treatment data may be given to the patient's personal physician or to other appropriate medical personnel responsible for the patient's welfare. Data generated as a result of the trial need to be available for inspection on request by the participating physicians, the sponsor's representatives, by the IRB / IEC and the regulatory authorities.

8.5.1 Collection, storage and future use of biological samples and corresponding data

Measures are in place to comply with the applicable rules for the collection, storage and future use of biological samples from clinical trial participants and the corresponding data, in particular

- A Quality Management System has been implemented to ensure the adherence with the Principles of Good Clinical Practice as outlined in 'Note For Guidance On Good Clinical Practice' (CPMP/ICH/13 5/95)
- The BI-internal facilities storing and analysing biological samples and data from clinical trial participants as well as the laboratories' activities for clinical trials sponsored by Boehringer Ingelheim are regularly audited. The analytical groups and the banking facility are therefore assessed to be qualified for the storage and use of biological samples and data collected in clinical trials.
- Samples and data are used only if an appropriate informed consent is available.

8.6 TRIAL MILESTONES

The **start of the trial** is defined as the date of the enrolment of the first patient in the whole trial.

The **end of the trial** is defined as the date of the last visit of the last patient in the whole trial (“Last Patient Out”).

The “**Last Patient Drug Discontinuation**” (LPDD) date is defined as the date on which the last patient at an individual trial site ends trial medication (as scheduled per protocol or prematurely). Individual investigators will be notified of SUSARs occurring with the trial medication until 30 days after LPDD at their site. **Early termination of the trial** is defined as the premature termination of the trial due to any reason before the end of the trial as specified in this protocol.

Temporary halt of the trial is defined as any unplanned interruption of the trial by the sponsor with the intention to resume it.

Suspension of the trial is defined as an interruption of the trial based on a Health Authority request.

The IEC / competent authority in each participating country will be notified about the trial milestones according to the respective laws.

Two separate clinical trial reports will be written for DINAMO™ and DINAMO™ Mono.

10. APPENDICES

10.1 TANNER STAGING MODIFIED

The evaluation of the Tanner stage will be performed during the physical examination at the time points defined in the [Flow Chart](#) to assess the patient's pubertal stage.

To determine the Tanner stage, the investigator should perform a brief check of external primary and secondary sex characteristics during the physical examination. The investigator will then score against the scale after the child has left the examination room. The most advanced pubertal stage will be documented.

Age appropriate explanations will be given, with emphasis that their privacy will be respected at all times. They will be reassured that their research records will be anonymised and only authorized trusted persons will monitor their notes to ensure the research is being conducted properly.

Here is a representation of the Tanner staging scale for both female and male children.

[figure not shown]

Figure 10.1: 1 Tanner Stages

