
planned end of the study. A descriptive Log-rank test will compare the linagliptin group and the empagliflozin group versus the placebo group individually up to Week 26.
 
The change in HbA1c from baseline to the end of 26 week will be analysed based on a REML approach using MMRM to assess the effectiveness and efficacy.
 
The change in HbA1c from baseline to the end of 26 week will also be analysed using an ANCOVA model including treatment as a fixed classification effect, baseline HbA1c as a linear covariate, and age as a categorical covariate. The secondary endpoints of change in FPG, body weight, SBP and DBP from baseline to the end of 26 week will be analysed in the same way as DINAMO™ with the DINAMO™ Mono data.
 
The proportion of patients who achieve HbA1c < 7.0% and < 6.5% at the end of 26 week will be determined per treatment group and the risk difference of active treatments versus placebo will be determined and assessed by an exact 2-sided 90% confidence interval.
			

FLOW CHART

Trial Periods	Screening	Placebo Run-in ¹	Randomised treatment period ⁴								Follow-up
	1A	1B	2 ²	3	4A	4B ³	5 ²	6	7	8 ² EOT ⁵	9 ¹³
Days calculated from the day of first (randomised) treatment	-21 to -14	-14	Day 1	29	85	99	183	211	295	365	386
Weeks from date of first randomised treatment			(**)	4	12	14	26	30	42	52	55
Time window for visits	+7 days ¹¹	+7 days ¹²	none	±7 days	±7 days	±7 days	±7 days	±7 days	±7 days	±7 days	+7 days
Informed consent and assent (*)	X										
Demographics	X										
Medical history	X										
Physical examination		X	X				X			X	X
Tanner staging (modified) ⁶			X				X			X	
Vital signs (seated) ¹⁴		X	X	X	X		X	X	X	X	X
12 lead-ECG		X					X			X	
Safety Laboratory tests ¹⁴	X ⁷		X ²	X	X		X ²	X	X	X ²	X
HbA1c ¹⁴	X		X	X	X		X	X	X	X	
PK blood sampling							X ⁸			X ⁸	
Fasting plasma glucose (FPG)			X ²				X ²			X ²	

FLOW CHART (cont.)

Trial Periods	Screening	Placebo Run-in ¹	Randomised treatment period ⁴								Follow-up
			2 ²	3	4A	4B ³	5 ²	6	7	8 ² EOT ⁵	
Visit	1A	1B	2 ²	3	4A	4B ³	5 ²	6	7	8 ² EOT ⁵	9 ¹³
Days calculated from the day of first (randomised) treatment	-21 to -14	-14	Day 1	29	85	99	183	211	295	365	386
Weeks from date of first randomised treatment			(**)	4	12	14	26	30	42	52	55
IGF-1, IGF-BP3 and markers of bone turnover ¹⁴			X	X ⁹			X	X ⁹		X	X
DPP-4 activity			X ¹⁰								
Pregnancy test ¹⁴	X		X	X	X		X	X	X	X	
Auto-antibodies for diabetes (IA-2 and GADA)	X										
Serum C-peptide	X		X ²				X ²			X ²	

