 - 4 Additional interactions (phone contact, text messaging or emails, as deemed appropriate) with the patient will be performed a day or two after randomised treatment started and then after 2, 8, 18, 22, 34, 38, 46 and 50 weeks of treatment. Visits 3, 4A, 6, 7, 9 can be done remotely/by telephone/telemedicine under exceptional circumstances due to the Corona Virus Disease-year 2019 (COVID-19) pandemic. Reasons a remote/telephone/telemedicine visit may be performed may include confirmed or suspected COVID-19 infection or unwillingness to return to the investigator site due to concerns of COVID-19 exposure.
 - 5 If a patient discontinues treatment early, an immediate End of Treatment (EOT) visit would be conducted.
 - 6 For patients with Tanner stage V at Visit 2, further assessment is not required at the subsequent visits.
 - 7 Laboratory tests at Visit 1A include TSH, liver enzymes, alkaline phosphatase, serum creatinine, cystatine C, haemoglobin and haematocrit only in addition to HbA1c and C-peptide and do not need to be collected in a fasted state.
 - 8 Blood samples for pharmacokinetic analysis will be collected within 30 minutes prior to drug administration at site (and preferably approximately 24 hours after drug administration on the previous day) and 1.5h ± 15 min after drug administration.
 - 9 IGF-1 and IGF-BP3 will not be measured at this Visit.
 - 10 Blood sample for DPP-4 activity measurement will be collected within 30 minutes prior to trial drug administration.
 - 11 Daily blood ketone measurements in the first 4 weeks of treatment and the 4 subsequent weeks after Visit 5; otherwise at least 3 times per week and in case of intercurrent illness/stress or if deemed necessary by the investigator. In addition, blood ketone levels will be checked by using the meter at clinic visits.
 - 12 Patients who complete an early End of Treatment visit and do not accept to attend all remaining planned visits will be contacted for vital status collection at Week 55. This can be done by phone.
 - 13 Patients who discontinue treatment early should attend Visit 9 at Week 55 in person or by telephone if agreed. At minimum, data on adverse events, concomitant therapies, and vital status should be collected at Visit 9 at Week 55.
 - 14 Vital signs, weight, and local laboratory testing is allowed for Visits 3, 4A, 6, 7, 9 under exceptional circumstances due to the COVID-19 pandemic.

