5.1.3 Further Endpoint(s)

5.1.3.2 Further endpoint to assess safety

Further endpoints to assess safety are listed below for both DINAMO™ and DINAMO™ Mono:

- Adverse events after 26 and 52 weeks, including adverse events of special interest (see [section 5.3.6.1](#)), genital infections, bone fracture, urinary tract infections, arthralgia, bullous pemphigoid, adverse events related to reduced intravascular volume, and ketone measurements reported as AE
- Percentage of patients with reported hypoglycaemia after 26 and 52 weeks
- Vital signs and heart rate after 26 and 52 weeks
- Change from baseline in Tanner staging after 26 and 52 weeks
- Change from baseline in serum electrolytes, hematology, biochemistry, lipids, IGF-1 and IGF-BP3 and markers of mineral and bone metabolism after 26 and 52 weeks
- Change from baseline in height (cm) and BMI (kg/m²) after 26 and 52 weeks
- Growth velocity (cm/year) after 26 and 52 weeks

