5.3.5.5 Tanner staging (modified)

Tanner staging is a scale of pubertal development in children, adolescents and adults which is routinely used for defining physical measures of development based on external primary and secondary sex characteristics, such as the size of the breasts, genitalia and development of pubic hair. Due to natural variation, individuals pass through the Tanner stages at different rates depending on the timing of puberty.

To assess the stage of puberty of each patient throughout the trial, a modified version of this scale will be used at the time points indicated in the Flow Chart. For patients with Tanner stage V at Visit 2, further assessment is not required at the subsequent visits. For details regarding the modified Tanner staging, please refer to [Appendix 10.1](#).

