Table 6.3: 1 Patient sets analysed and treatment groupings (continued)

Class of endpoint	Patient sets					
	SCR	TS	TSactive	RS	mITT	PPS
Secondary efficacy endpoints						
Change in FPG [mg/dl] from baseline - ANCOVA					OC-AD-BOCF; OC (TG1)	
Change in body weight [kg] / SBP [mmHg] / DBP [mmHg] from baseline – MMRM					OC-AD; OC (TG1)	
Proportion of patients who achieve HbA1c goals < 6.5% and < 7.0%. Exact CI					NCF; OC (TG1)	

Table 6.3: 1 Patient sets analysed and treatment groupings (continued)

Class of endpoint	Patient sets					
	SCR	TS	TSactive	RS	mITT	PPS
Further safety endpoints						
Shift tables for the Tanner staging score from baseline		OC-AD (TG1, TG5)				
Descriptive statistics over time for growth velocity		OC-AD (TG1, TG5)				
Safety evaluation						
Overall summary of AEs		TG1, TG5, TG4	TG6			
Freq. of patients with the following AEs by treatment, SOC and PT 
 
• AEs
 
• AEs by worst intensity
 
• Drug-related AEs
 
• AEs leading to treatment discontinuation
 
• SAEs
 
• Other significant adverse events
 
• AESIs(except DKA and lower limb amputation)
 
		TG1, TG5, TG4	TG6			
Incidence rate of patients with AEs by treatment, SOC and PT		TG1, TG5				
List of patients with AESIs/other significant AE 
 
• DKA
 
• Events involving lower limb amputation
 
• Bone fracture
 
		TS				
Freq. of patients with other specific AE by treatment, SOC and PT: 
 
• Hypoglycaemic AE
 
• UTI (also investigator assessment, serious and leading to treatment discontinuation)
 
• Genital infection (also investigator assessment, serious and leading to treatment discontinuation)
 
• Acute pyelonephritis or urosepsis
 
• Volume depletion
 
• Ketone measurements
 
		TG1, TG4	TG6			

Table 6.3: 1 Patient sets analysed and treatment groupings (continued)

Class of endpoint	Patient sets					
	SCR	TS	TSactive	RS	mITT	PPS
Freq. of patients with other specific AE by treatment, SOC and PT: 
 
• Arthralgia
 
• Pemphigoid in bullous conditions)
 
		TG1	TG6			

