#### 6.6.4 Missing and incomplete laboratory reference ranges

Incomplete (one-sided) laboratory reference ranges are imputed according to BI standards (see “Handling of incomplete reference ranges”) ([14](#)).

In case of serum N-terminal cross-linked telopeptide (NTx), central lab reference range was not included in the data transfer as it was based on the Tanner stage score. The Tanner stage score was unknown to the central lab. This missing central lab reference range will be incorporated in the Analysis Data Model (ADaM) dataset based on the Tanner stage score according to the central lab reference ranges ([15](#)).

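### Only the most advanced Tanner component is recorded, so a pubertal delay confined to a component that is level with or behind the other cannot be seen

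*Protocol*

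**What the plan says.** Protocol Section 5.3.5.5 describes a scale built on several characteristics, "such as the size of the breasts, genitalia and development of pubic hair". Appendix 10.1 asks for a brief check of these during the physical examination, scored after the child has left the room, and then: "The most advanced pubertal stage will be documented". The Flow Chart schedules the assessment at Visits 2, 5 and 8 (Day 1, Week 26 and Week 52).

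Flow Chart footnote 6 and Section 5.3.5.5 carry the same exemption: "For patients with Tanner stage V at Visit 2, further assessment is not required at the subsequent visits".

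The endpoint in Protocol Section 5.1.3.2 is "Change from baseline in Tanner staging after 26 and 52 weeks", with no direction stated. SAP Table 6.3: 1 analyses it as "Shift tables for the Tanner staging score from baseline" on the treated set, using all available data, for treatment grouping 1 (TG1: placebo, linagliptin and pooled empagliflozin to Week 26) and treatment grouping 5 (TG5: linagliptin and pooled empagliflozin to Week 52, without placebo).

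No component-level record or table appears in the text available. The same single score supplies the NTx reference range (SAP 6.6.4: "This missing central lab reference range will be incorporated in the Analysis Data Model (ADaM) dataset based on the Tanner stage score") and the Tanner subgroups for PINP, NTx, IGF-1 and IGF-BP3 (SAP 7.8.2.5).

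**The concern.** If one value is kept per visit and it is the highest across components, the record behaves as a maximum. A maximum does not respond when something below or level with the top slows down, provided the other component carries on. A child whose breast or genital development stalls while pubic hair advances on schedule, from the same or a higher stage, gets the same recorded stage as an unaffected child.

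Pubertal development is a named safety endpoint in patients aged 10 to 17. A table without imbalance could be read as showing normal development in each component, which the recorded data cannot establish. The Visit 2 exemption adds a smaller gap: a child at V on one component and below V on the other is recorded as V, and later staging is not required.

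**Working it through.** The plan states no expected shift, rate or precision for Tanner stage, so there is no figure of its own to reproduce. The check is a count of cases under the recording rule.

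**From the documents:** one recorded value per visit, the most advanced; a scale with several components; staging at Visits 2, 5 and 8; later staging not required if the recorded stage is V at Visit 2.

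**Assumptions, not from the documents:** two components with stages a and b from 1 to 5; recorded stage = max(a, b); unaffected progress of +1 stage per interval, capped at 5; delay = +0; acceleration = +2; component a is the affected one; the baseline gap |a − b| is at most 0, 1 or 2.

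**Delay in component a only.** Unaffected record: max(a+1, b+1). Record with delay: max(a, b+1). They differ only if a > b.
- Example, level: (2, 2) gives max(2, 3) = 3 against max(3, 3) = 3. Not visible.
- Example, affected component ahead: (3, 2) gives max(3, 3) = 3 against max(4, 3) = 4. Visible.

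**Acceleration in component a only.** Record: max(a+2, b+1). It differs from the unaffected record only if a ≥ b. The component can show a change at all only if a ≤ 3, because a component at 4 reaches the cap under normal progress.

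**Delay in both.** Record: max(a, b) against max(a, b) + 1. These always differ below V.

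Counts of stage pairs in which the recorded stage changes, among pairs with max(a, b) < 5 at Visit 2:

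| Largest baseline gap | Delay in one | Acceleration in one | Delay in both |
|---|---|---|---|
| 0 | 0 of 4 | 3 of 3 | 4 of 4 |
| 1 | 3 of 10 | 5 of 8 | 10 of 10 |
| 2 | 5 of 14 | 6 of 11 | 14 of 14 |

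As a check on the second row, the 3 visible delays are (2,1), (3,2) and (4,3). The other 7 of the 10 pairs are the 4 level pairs and the 3 in which the affected component is behind.

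**Exempt at Visit 2.** Pairs with one component at 5 and the other below are (5,4) and (4,5) for a gap up to 1, plus (5,3) and (3,5) for a gap up to 2. All are recorded as V, so nothing later can appear if staging stops.

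These are counts of possible pairs, each given equal weight. They show which cases the rule hides, not how many patients are affected.

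**The case against.** A reader might infer that the endpoint is one-sided and cannot show delay. The documents do not support that. If puberty slows in all components, the maximum stops rising and the TG1 table shows fewer upward shifts than placebo. Acceleration can be hidden too, when it affects a lagging component. Nothing in the documents gives a reason why either drug would slow one component and spare the other.

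A reader might also infer that reaching stage V at any time ends assessment. It does not. The exemption concerns stage V at Visit 2 and says only that later staging is not required; a child first reaching V at Week 26 is still scheduled at Week 52.

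Tanner change is one of several further safety endpoints, and safety analyses are descriptive without hypothesis testing (Protocol 7.3.6). Development is also followed through "Growth velocity (cm/year) after 26 and 52 weeks", height, IGF-1 and IGF-BP3. These do not replace component staging, but the plan does not rest on this score alone.

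The Tanner figure, SAP Table 6.4: 1 and the eCRF are not available, so a component-level record could exist outside the visible text. Appendix 10.1 as written does not call for one.

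These points narrow the concern. They leave standing that, under the stated rule, a delay in a level or lagging component has no route into the planned table.

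**Conclusion.** The point holds in a limited form. A delay confined to a component level with or behind the other cannot be seen in the Tanner endpoint. A delay in the leading component may show, and an overall delay does show against placebo up to Week 26. The Visit 2 exemption can also remove a child from later staging while one component is still below V.

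No reliable patient percentage can be given: it would depend on how often components agree at baseline and on the ceiling at V, and the documents inform neither. It may be tempting to extend the point to the NTx reference range and the bone-marker subgroups, but no resulting error has been shown there.

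The conclusion assumes that most advanced means the highest stage across components, which is the natural reading but is not spelled out. At Week 52 the TG5 table has no placebo group, so a delay there is hard to interpret under any recording rule. This is an inexpensive improvement to a descriptive safety endpoint and does not affect the efficacy conclusions.

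**What to change.** - **Appendix 10.1 and the eCRF:** record the breast stage (girls) or genital stage (boys) and the pubic-hair stage as two values at each Tanner assessment. The cost is one more field per assessment. The characteristics are already inspected, so no additional examination is needed in children still being staged.
- **SAP Table 6.3: 1:** give the Tanner shift tables by component for TG1 and TG5, noting that TG5 has no placebo group. Keep the maximum as an extra table and for the NTx range.
- **Optional, Flow Chart footnote 6 and Section 5.3.5.5:** limit the Visit 2 exemption to children with both components at V. The downside is a repeated brief but intimate check at Visits 5 and 8 in a few adolescents who are now exempt. A physical examination is already scheduled at those visits.
- **Visits already completed:** Section 5.3.1 requires physical examination results in the source documents but does not say that component stages are among them. Use them where they exist. Otherwise, state in the report that a single-component delay could not be assessed.

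The prospective changes need a protocol amendment. The statement in the report does not.
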